2.5.2 Study ending or halting due to safety

Subjects will be under medical supervision for the duration of this study and their health will be the top priority. Study physicians will be primarily responsible for evaluating a subject's medical condition. Study complications that may adversely affect a subject's health will consequently lead to the removal of the electrodes and ending of a subject's participation. Complications that could result in the removal of stimulation leads include:

- Lead migration that prevents the evocation of sensation in the missing limb
- Lead breakage
- Signs of systemic infection
- Unresolved local infection at the lead site
- Changes in subject's medical status that could affect eligibility
- Non-compliance with study procedures, including temperature monitoring, care of the implant sites, and attending testing sessions and clinical exams

We may halt the study and reevaluate our protocol and risk mitigation procedures due to the occurrence of multiple adverse events. Adverse events that could result in the halting of the study and re-evaluation of study protocol include:

- Two incidents of unresolved superficial infection resulting in lead removal
- One incident of deep infection
- One or more inpatient hospitalizations of subjects
- Two or more subjects who withdraw from the study due to worsening pain or intolerable dysesthesia
- One or more subjects who suffer a fracture due to falls related to the study interventions

2.5.3 Sample size determination

A maximum of 15 participants will be enrolled in order to achieve a maximum of 10 subjects undergoing study procedures. Because it is possible that a subject may enroll and then be determined to be ineligible for placement of the spinal cord stimulator leads, the maximum number of subjects enrolled may exceed the number of subjects who undergo lead placement.

This is one of the first studies to evaluate sensory perceptions during spinal cord stimulation in lower-limb amputees. Because this is a feasibility study, we feel that it is appropriate to begin with a small sample size in this initial investigation.

2.5.4 Outcome data and data analysis

The primary outcome measure of the study will be safety. We will track the rate of adverse events to monitor safety of the study. The primary efficacy outcome will be quantification and evaluation of the types of sensory percepts evoked by spinal root stimulation, as well as the anatomical locations to which those percepts are referred. Additionally, we will record any subjective changes in the perception of phantom limb sensations or phantom limb pain during and following spinal root stimulation. We will quantify differences in the ability to control a prosthetic limb with and without sensory stimulation. We will compare the balance and gait assessment scores of individuals using the SCS-LLA system and community-use of stimulation with the scores of subjects who underwent lab-only testing in our ongoing study to quantify the effects of extended access to the device.

New information will be learned with each participant, as this is a pilot study. Single-subject design statistical analyses will be used. Our main goals are to demonstrate device safety as well as the feasibility of using spinal root stimulation to evoke realistic sensory percepts referred to the foot and leg in individuals with lower-limb amputation, and to document any effects of that stimulation on phantom limb sensations and phantom limb pain. We will quantify the threshold for producing a just-noticeable sensory percept, as well as the relationships between stimulation parameters and evoked sensations when stimulating through individual electrodes or combinations of multiple electrodes.

To fulfill Specific Aim 1, we will document adverse events that occur during the study. We will report adverse events to the local Institutional Review Board and to the FDA in accordance with the respective reporting requirements. This documentation will serve as demonstration of the safety of the SCS-LLA system in this small sample.

To fulfill Specific Aim 2a, in which we quantify the threshold for evoking a sensory percept, we will use regression analysis to examine differences in stimulation thresholds related to a variety of factors. Examples of these factors include the anatomical location of each electrode (based on fluoroscopic imaging), level of amputation, time since amputation, level of pre-intervention phantom limb sensation and pain, and the thresholds of nearby electrodes.

With respect to Specific Aim 2b, the results will produce descriptive anatomical maps of the modalities and locations of sensory percepts evoked by spinal root stimulation. These maps will allow us to examine the specificity of stimulation through individual electrodes as well as the overall coverage of the evoked sensory percepts across the entire amputated limb. The results of Specific Aim 2c will be a set of purely descriptive statements made by the subjects that will provide additional insight into their experience with SCS and their preferences for this type of neuroprosthetic intervention.

The results of Specific Aims 3a and 3b will be a combination of descriptive statements on the subjective experience of SCS and its effects on phantom limb sensations and pain, as well as a data set including perceived pain ratings from a visual analog scale at multiple time points before and during the experimental study. These pain-rating results will be

compared within each subject and across subjects via regression analysis to determine if there is any effect of spinal root stimulation on phantom pain levels.

The results of Specific Aims 4 and 5 will be a data set including EMG, kinematics, and performance metrics that will allow us to quantify the subject's ability to control a prosthetic limb with and without sensory stimulation. Kinematic and performance metrics data will be compared within and across subjects using regression analysis to quantify changes in control with the addition of sensory stimulation.

With respect to Specific Aim 6, we will utilize analysis of variance to compare balance, gait, and pain scores before and after the trial of community use.

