
1.3 Objectives of the clinical investigation

The proposed clinical investigation is a feasibility study directed toward the following aims:

Specific Aim 1: Demonstrate the safety of the SCS-LLA system over a period of up to 90 days. We will monitor adverse events throughout the study, and these results will provide supporting data for future studies with larger cohorts and a fully implanted SCS system.

Specific Aim 2: Characterize the sensations evoked by lumbar epidural spinal root stimulation in lower-limb amputees.

- **Specific Aim 2a:** Quantify the threshold (minimum charge and pulse rate) stimulus required to evoke sensory percepts and neurophysiological responses (e.g. reflexive EMG responses) during SCS, and monitor changes in those percepts and responses over time. These results will provide insight into the design requirements for a future SCS system, as well as a point of comparison among subjects and with other studies in the scientific literature. Additionally, the stability of the responses will provide insight into the feasibility of long-term use of the device.
- **Specific Aim 2b:** Evaluate the relationship between stimulation parameters (e.g. pulse width, pulse amplitude, stimulus location, etc.) and the modality and naturalness of perceived sensations. Lumbar SCS can evoke paresthesia referred to the amputated limb, but our goal is to produce meaningful (non-paresthetic) sensations. As we expect the stimulation parameters to have significant effects on the evoked sensations, we will perform standardized psychophysical examinations to determine the relationship between stimulation parameters and perceived sensations. These tests will be repeated at multiple points throughout the study to observe any changes that occur over multiple days of use.
- **Specific Aim 2c:** Document the subjective perception of lower-limb amputees of lumbar SCS for restoration of sensation. To achieve widespread adoption of a sensory neuroprosthesis, it will be crucial for amputees to perceive significant value from the device. As such, we will ask each subject to provide subjective feedback on their perceived utility of the sensory feedback provided by the device.

Specific Aim 3: Characterize the effects of lumbar SCS on phantom limb sensations and phantom limb pain in lower-limb amputees. This aim is secondary to the primary study goals in Aims 1 and 2, and as such, we will not exclude individuals that do not experience phantom limb pain.

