2.3.2 Anticipated number of research subjects

Up to 15 total subjects may undergo research procedures, with the goal of completing all experiments with 10 subjects. Recruitment rates will be monitored by our DSMB. Because it is possible that a subject may enroll and then be determined to be ineligible, the

maximum number of subjects enrolled may exceed the number who undergo device placement. Subjects will be enrolled as necessary to maintain the target number of subjects. Recruitment will not begin until we have received all approvals.

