2.5 Study outcome evaluations

2.5.1 Study endpoints

The SCS leads will be removed no later than 90 days after implantation. The primary safety endpoint will be that there are no serious device-related adverse events. The secondary safety endpoint will be to determine the type and frequency of device-related

adverse events measured of the 90-day period following implantation. The primary efficacy endpoint for this study will be demonstration of the ability to evoke sensations localized to at least three focal regions of the missing foot and shank (e.g. lateral forefoot, medial forefoot, and heel). The secondary efficacy endpoints will be an improvement in balance control and gait stability and a reduction in phantom limb pain. Balance control and gait stability will be measured by a 10-point improvement in the Sensory Organization Test or a 6-point improvement in Functional Gait Assessment. A reduction in phantom limb pain will be measured by a 5-point improvement in the McGill Pain Questionnaire.

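### The plan promises to demonstrate safety but attaches no interval or denominator to its zero-event endpoint; no events in 10 subjects would leave a true risk of up to 26–31% open

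*Combined protocol and SAP*

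**What the plan says.** **Endpoint (2.5.1).** "The primary safety endpoint will be that there are no serious device-related adverse events". The secondary safety endpoint is the type and frequency of device-related events over the 90 days after implantation.

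**Objective (1.3, Aim 1).** "Demonstrate the safety of the SCS-LLA system over a period of up to 90 days". The aim adds that the results are meant to support later studies with larger cohorts and a fully implanted system.

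**Analysis (2.5.4).** Safety is the primary outcome measure. Three sentences matter:
- "We will track the rate of adverse events to monitor safety of the study"
- "Our main goals are to demonstrate device safety as well as the feasibility" (the sentence continues with the sensory aims)
- "This documentation will serve as demonstration of the safety of the SCS-LLA system in this small sample"

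Only the last of these is limited to the sample studied.

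**Number of subjects.** Section 2.5.3: "A maximum of 15 participants will be enrolled in order to achieve a maximum of 10 subjects undergoing study procedures". Section 2.3.2: "Up to 15 total subjects may undergo research procedures, with the goal of completing all experiments with 10 subjects". The size is justified only by the feasibility character of the study. No event rate, acceptable risk or precision target is given.

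**The concern.** Safety is the primary outcome, and its endpoint is the absence of a serious device-related event in a very small group. A count of zero carries limited information at this size. Without an interval, a reader of the final report would see zero events beside an objective to demonstrate safety, with nothing to show how large a risk remains possible.

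Aim 1 says that the results are to support larger and fully implanted studies, so the use intended for them goes beyond the subjects treated. The exposure is also partly new: section 3.1 expects infection risk to be higher than the manufacturer's figures because the leads stay percutaneous for longer.

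The denominator is open as well. Section 2.5.2 lists reasons for early lead removal, several of them complications. A proportion based on completers could leave out the very subjects who had events.

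**Working it through.** The plan has no calculation to reproduce. The check asks what zero events would show.

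**Inputs**
- Events: 0 (the endpoint in 2.5.1).
- Subjects: 10 (2.5.3) or 15 (upper figure in 2.3.2).
- Confidence level: 95%. This is an assumption; the documents state none.
- Subjects are treated as independent with a common risk p of at least one serious device-related event.

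**Step 1: exact (Clopper-Pearson) upper limit for 0 of n**

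One-sided: 1 − 0.05^(1/n). Two-sided: 1 − 0.025^(1/n).

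| n | One-sided 95% | Two-sided 95% |
|---|---|---|
| 10 | 1 − 0.05^(1/10) = 25.9% | 1 − 0.025^(1/10) = 30.8% |
| 15 | 1 − 0.05^(1/15) = 18.1% | 1 − 0.025^(1/15) = 21.8% |

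The rule of three (3/n) gives 30% and 20%, which agrees.

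**Step 2: chance of observing no event, (1 − p)^n**

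| True risk p | n = 10 | n = 15 |
|---|---|---|
| 2% | 0.98^10 = 82% | 0.98^15 = 74% |
| 5% | 0.95^10 = 60% | 0.95^15 = 46% |
| 10% | 0.90^10 = 35% | 0.90^15 = 21% |
| 20% | 0.80^10 = 11% | 0.80^15 = 4% |

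The endpoint is imprecise in both directions. With 10 subjects it would be missed 18% of the time at a true risk of 2%, and met about a third of the time at 10%.

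**Step 3: the scale of evidence needed**

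For zero events to bring the one-sided 95% upper limit down to 10%, n must be at least ln(0.05)/ln(0.90) = 28.4, so 29 subjects. For 5% it is ln(0.05)/ln(0.95) = 58.4, so 59. These figures only show the distance between the design and the word *demonstrate*; they are not a request for more subjects.

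**Step 4: which n applies**

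Section 2.5.3 caps subjects undergoing study procedures at 10. Section 2.3.2 allows 15 to undergo research procedures, with 10 completers as the goal. The two do not agree, and neither states outright how many will have leads placed. Over 10 to 15 subjects, the upper limit after zero events runs from 30.8% (n = 10, two-sided) to 18.1% (n = 15, one-sided).

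**The case against.** The strongest reply is that the study does not claim much. Section 2.2.1 calls the design descriptive, and 1.3, 2.5.3 and 2.5.4 call the study a feasibility or pilot study. Small numbers are normal at this stage. The frequency of device-related events by type is already a secondary endpoint. Halting criteria (2.5.2) and an independent monitoring board (4.4) protect subjects whatever the endpoint says.

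Much of this stands, and it rules out three stronger readings that a reader might infer:

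- *That the plan declares success on 0 of 10.* It does not. Section 2.5.1 names an endpoint, and no section ties a zero count to a formal conclusion or a go/no-go step. The hedged sentence in 2.5.4 attaches the demonstration to the documentation of events, whatever their number.
- *That zero events is likely even at an unacceptable risk.* The documents set no threshold of acceptable risk. With 10 subjects, zero events is more likely than not only when the true risk is below 1 − 0.5^(1/10) = 6.7%. What can be said is that zero events does not exclude a substantial risk.
- *That the true risk is 26–31%.* These are upper limits on two conventions, not an estimate of the risk.

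The rest of the reply does not remove the point. The halting criteria and the board govern conduct, not what a clean final result means. The secondary endpoint has no interval either. The feasibility label does not qualify the wording of Aim 1 or of the main-goals sentence.

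**Conclusion.** The point holds as one of wording and reporting. The plan promises without qualification, in two places, to demonstrate safety, and it specifies neither an interval nor a denominator for the primary safety endpoint. A result of zero events would leave a per-subject risk of up to 25.9% or 30.8% open with 10 subjects, and up to 18.1% or 21.8% with 15 (one-sided and two-sided respectively).

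This rests on an assumed 95% level, on independent subjects with a common risk, and on a count of subjects rather than events. The conclusion is the same at either sample size. If fewer than 10 subjects had leads placed, the limits would be higher.

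The point should be corrected because it concerns the primary outcome and the correction is small. It is not an argument that the study is too small for its purpose.

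**What to change.** 1. **In 2.5.1 and 2.5.4, define the summary.** Report the number of subjects with at least one serious device-related adverse event over all subjects who had leads placed, including those whose leads were removed early, with an exact (Clopper-Pearson) 95% interval.
2. **Extend it to the secondary safety endpoint.** Give the same interval for each type of device-related event already planned there.
3. **Reword the claim in 1.3 (Aim 1) and in both sentences of 2.5.4.** Use *estimate the event risk* or *obtain preliminary data on safety* in place of *demonstrate* and *demonstration*.
4. **State in advance what zero events would mean.** Give the upper limit for the number of subjects actually implanted rather than fixing one figure; for orientation, it is about 18–31% across 15 to 10 subjects. Say whether the limit is one-sided or two-sided.
5. **Reconcile 2.3.2 and 2.5.3** on whether up to 15 or at most 10 subjects may undergo procedures, and state how many are expected to have leads placed.

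The cost is some rewording and one line of analysis. No extra subjects or assessments are needed. The downside is that the stated safety conclusion becomes less favourable.

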2.2 Study design

2.2.1 General study design

This study is a prospective, non-randomized, open-label, descriptive, interventional study.

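### Aim 2a: the threshold regression names neighbouring contacts' thresholds as a predictor, and mixes contact-level with subject-level factors without stating a unit of analysis

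*Combined protocol and SAP*

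**What the plan says.** Section 2.5.4 states for Aim 2a that "we will use regression analysis to examine differences in stimulation thresholds related to a variety of factors". Its examples begin with the anatomical location of each electrode and continue with "level of amputation, time since amputation, level of pre-intervention phantom limb sensation and pain, and the thresholds of nearby electrodes". Location and nearby thresholds vary from contact to contact. Amputation level, time since amputation and baseline phantom sensation and pain each have one value per subject.

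The only general statement on the form of analysis is in the same section: "Single-subject design statistical analyses will be used". Section 2.4.2.10 provides for one to three leads of eight contacts. Section 2.3.2 says "Up to 15 total subjects may undergo research procedures, with the goal of completing all experiments with 10 subjects". Under Aim 2a, section 1.3 intends to "monitor changes in those percepts and responses over time" and offers the results "as well as a point of comparison among subjects and with other studies in the scientific literature".

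No section names the unit of analysis, a random effect, a robust standard error, a covariance structure, or averaging to one value per contact or subject.

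**The concern.** There are two linked problems.

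The first is in the stated text. A nearby electrode's threshold is itself an outcome in the same data set. Entering it as a predictor makes each row's outcome explain its neighbour's, and the reverse. The usual standard error is then wrong. The coefficient also picks up whatever two contacts share through belonging to one person, so it competes with the subject-level factors that the plan wants to study.

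The second is an omission. Subject-level factors carry information from about 10 people, not from 80 to 240 contacts. Single-subject analyses cannot estimate a factor that is constant within the subject, so subjects must be pooled, and the plan does not say how.

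At stake is whether chance differences among about 10 people, or an artefact of the neighbour term, are reported as determinants of threshold and then compared with other studies.

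**Working it through.** The plan gives no alpha, correlation, standard deviation or sample-size figure for Aim 2a, so there is no stated figure to reproduce.

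**Inputs from the documents.** Contacts per subject: 1 × 8 = 8 to 3 × 8 = 24 (section 2.4.2.10). Subjects: 10 (goal in 2.3.2; maximum in 2.5.3). Rows at one time point: 10 × 8 = 80 to 10 × 24 = 240.

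**Assumptions.** Two-sided 5% test, normal data, one threshold per contact, and within-subject correlation ρ of 0, 0.05 or 0.3. A nearby threshold is the mean of the adjacent contacts on the lead, with one neighbour for an end contact.

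**Step 1: neighbour predictor, ρ = 0, rows treated as independent.** Each adjacent pair enters twice, once with each contact as outcome. On a lead of 8 with unit variance, the slope's numerator collects 5 interior pairs with weight ½ + ½ = 1 and 2 end pairs with weight 1 + ½ = 1.5.
- True variance: 5 × 1² + 2 × 1.5² = 9.5.
- Variance that least squares assumes: 6 × 0.5 + 2 × 1 = 5.
- Ratio: 9.5/5 = 1.9, so the standard error is too small by √1.9 = 1.38.
- Rejection rate: 2 × [1 − Φ(1.96/1.38)] = 15.5%.

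Simulations with 8 to 24 contacts give 15–17%.

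**Step 2: neighbour predictor with correlation, and with subject effects.** With no local effect, simulated rejection is about 17–24% at ρ = 0.05 and 69–92% at ρ = 0.3, because neighbours share a subject. Adding subject effects leaves 17–43%, depending on the number of contacts, ρ and how the effect is fitted. Removing the mean of m contacts forces a correlation of −1/(m − 1) between deviations: −1/7 = −0.14 for m = 8 and −1/23 = −0.04 for m = 24. The test reads this as a neighbour effect.

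**Step 3: absorption of a subject-level effect.** Suppose the true coefficient is β = 0.50 and ρ = 0.3. Given the subject-level factor:
- Covariance of a threshold with its neighbours' mean: 0.3.
- Average variance of that mean: 0.3 + 0.7 × (6 × 0.5 + 2 × 1)/8 = 0.3 + 0.7 × 0.625 = 0.7375.
- Neighbour coefficient: γ = 0.3/0.7375 = 0.41.
- Remaining coefficient on the factor: β(1 − γ) = 0.50 × 0.59 = 0.30 with many subjects.

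Simulated with 10 subjects, the coefficient is about 0.34. Without the neighbour term it stays at 0.50.

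**Step 4: subject-level factor, contacts treated as independent, no neighbour term.** The design effect is DE = 1 + (m − 1)ρ, and the approximate rejection rate is 2 × [1 − Φ(1.96/√DE)].

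| m | ρ | DE | Rejection |
|---|---|---|---|
| 8 | 0.05 | 1.35 | 9% |
| 24 | 0.05 | 2.15 | 18% |
| 8 | 0.3 | 3.1 | 27% |
| 24 | 0.3 | 7.9 | 49% |

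Simulation gives 9–20% at ρ = 0.05 and 28–52% at ρ = 0.3. With 15 subjects the rates are 9–19% and 27–50%. Regression on 10 subject means gives 4.6–5.5%.

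**Step 5: is a plain mixed model enough?** Not if adjacent contacts are more alike than distant ones. With lead intercepts removed, no true effect and an assumed adjacent-contact correlation of 0.2, 0.3 or 0.5, a test of position along the lead rejects 9%, 11% and 19% of the time (one lead) or 9%, 12% and 17% (three leads). At zero correlation it rejects 4.5–5.1%. A spatial term is therefore needed.

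**The case against.** The strongest reply is that this is missing detail and not error. Regression analysis includes mixed models, the factors are only examples, and no alpha or hypothesis is attached to Aim 2a. Section 2.2.1 says "This study is a prospective, non-randomized, open-label, descriptive, interventional study". The wording for the other aims in 2.5.4 is equally brief.

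Much of this stands. A reader might infer that the plan commits to treating contacts as independent; it does not say so, and the rates in step 4 apply only if that is done. A reader might also infer that every session will be pooled as a further row, or that electrode location differs systematically between subjects. The documents establish neither. Thresholds are to be followed over time, but no section says that all sessions enter this regression. Leads are adjusted for each subject, but no between-subject spread in location is given. Nothing here rests on either inference.

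The reply does not reach the neighbour predictor. It is named in the text, and neither the independent-row analysis nor the addition of subject effects makes it sound. The single-subject statement does not help with subject-level factors, which do not vary within a person.

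**Conclusion.** The point holds in two parts of different strength.

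- **Neighbour thresholds as a predictor:** unsound as written. The false-positive rate is about 15–17% in the most favourable case (zero correlation), and stays at 17–43% with subject effects. At an assumed correlation of 0.3 a true subject-level effect of 0.50 shrinks to about 0.34.
- **Unit of analysis:** unspecified. If contacts are treated as independent, subject-level factors reject about 9–20% of the time at correlation 0.05 and 28–52% at 0.3.

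All figures assume a nominal 5% test, normal data and 10 subjects. The correlations are assumed. Even the lowest non-zero value, 0.05, roughly doubles to quadruples the error rate for subject-level factors.

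The scope is the exploratory Aim 2a regression. A reader might infer a threat to the main conclusions, but the safety and efficacy endpoints in section 2.5.1 do not use this regression.

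**What to change.** In section 2.5.4, for Aim 2a:

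- Remove nearby thresholds from the predictors and report them as a within-lead correlation.
- For contact-level factors, specify a mixed model with random effects for subject, for lead within subject (where there is more than one) and for electrode, plus a within-lead spatial correlation for adjacent contacts.
- Analyse subject-level factors on one value per subject, about 10 points, labelled exploratory.

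This full model has not been simulated here. With about 10 subjects it may not support every term, so the plan should also state the order in which terms are dropped if it does not converge.

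The cost is a few sentences, a little more analysis work on data already planned, and wider intervals. No new visits, measurements or subjects are needed.
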